3.6.1.3 Physical Examination

A complete physical and neurologic examination will be performed at the time of the initial and final study Visit, as well as during the early termination Visit, if applicable. Abnormalities in the examination appreciated during Visit 1 and reflective of the subject's known dystonia will be recorded and labeled as non-clinically significant. Any and all changes in the examination happening during the course of the trial will be recorded and reported, when appropriate. Figure 2 below shows the form that will capture this data.

	Figure 2	
Date: DD – MMM – YYYY		Study subject number:

Visit Number (circle one): 15 Early termination Visit

The AUDYT Trial Physical Exam Form

Vital signs	s: BP:  / 	WT:lbs
General examination		
Skin:	Normal Abnormal – CS Abnormal – NCS	If abnormal, describe:
Cardiovascular:	Normal Abnormal – CS Abnormal – NCS	If abnormal, describe:
Respiratory:	Normal Abnormal – CS Abnormal – NCS	If abnormal, describe:
Abdomen:	Normal Abnormal – CS Abnormal – NCS	If abnormal, describe:
Extremities:	Normal Abnormal – CS Abnormal – NCS	If abnormal, describe:
Neurologic examination Mental Status:	Normal Abnormal – CS Abnormal – NCS	If abnormal, describe:
Cranial Nerves:	Normal Abnormal – CS Abnormal – NCS	If abnormal, describe:
	Normal Abnormal – CS Abnormal – NCS	If abnormal, describe:
Cerebellar:	Normal Abnormal – CS Abnormal – NCS	If abnormal, describe:
Reflexes:	Normal Abnormal – CS Abnormal – NCS	If abnormal, describe:

Gait:	Normal	If abnormal, describe:
	Abnormal – CS	
	Abnormal – NCS	

3.6.1.4 Vital Signs and Weight

Vital Signs (including weight) will be measured and recorded during all scheduled study Visits, including the early termination Visit, if such a Visit happens. Any and all gross abnormalities or significant changes will be reported. Figure 3 shown below shows the form that will capture this data.

Figure 3

Date: DD – MMM – YYYY Study subject number: ____

Visit Number (circle one): 2 3 4

The AUDYT Trial Vital signs Form

Vital signs: BP: ___/ HR: ___ RR: ___ WT: ___lbs

3.6.1.5 Columbia Suicide Severity Rating Scale

Suicidal thoughts or actions are a possible side effect of AUSTEDO use. The rater/clinician-administered versions of the Columbia-Suicide Severity Rating Scale (C-SSRS)¹⁷ for research (http://cssrs.columbia.edu/the-columbia-Scale-c-ssrs/cssrs-for-research/) assess severity and intensity of suicidal ideation, types of suicidal behaviors, and lethality of suicide attempts at time points and over time periods that are typical for randomized control trials. The Columbia Suicide Severity Rating Scale

will be administered during all scheduled study Visits, including the early termination Visit, if such a Visit happens. Development of suicidality as determined by this instrument at any point during the trial will warrant the immediate discontinuation of the study drug, as well as psychiatric care as determined necessary by the investigator. Subjects with any signs of suicidality during Visit 1 as detected by the scale will be immediately excluded from participating in the trial. Figure 4 shown below shows this Scale embedded in a data capture form:

	Figure 4	
Date: DD – MMM – YYYY		Study subject number:

Visit Number (circle one): 1 2 3 4 5 Early termination Visit

The AUDYT Trial

Columbia Suicide Severity Rating Scale

SUICIDAL IDEATION		
Ask questions 1 and 2. If both are negative, proceed to "Suicidal Behavior" section. If the answer to question 2 is "yes", ask questions 3, 4 and 5. If the answer to question 1 and/or 2 is "yes", complete "Intensity of Ideation" section below.		e Last isit
1. Wish to be Dead Subject endorses thoughts about a wish to be dead or not alive anymore, or wish to fall asleep and not wake up. Have you wished you were dead or wished you could go to sleep and not wake up? If yes, describe:	Yes	No
2. Non-Specific Active Suicidal Thoughts General, non-specific thoughts of wanting to end one's life/commit suicide (e.g., "I've thought about killing myself") without thoughts of ways to kill oneself/associated methods, intent, or plan during the assessment period. Have you actually had any thoughts of killing yourself? If yes, describe:	Yes	No
3. Active Suicidal Ideation with Any Methods (Not Plan) without Intent to Act Subject endorses thoughts of suicide and has thought of at least one method during the assessment period. This is different than a specific plan with time, place or method details worked out (e.g., thought of method to kill self but not a specific plan). Includes person who would say, "I thought about taking an overdose but I never made a specific plan as to when, where or how I would actually do itand I would never go through with it." Have you been thinking about how you might do this? If yes, describe:	Yes	No
4. Active Suicidal Ideation with Some Intent to Act, without Specific Plan Active suicidal thoughts of killing oneself and subject reports having some intent to act on such thoughts, as opposed to "I have the thoughts but I definitely will not do anything about them." Have you had these thoughts and had some intention of acting on them? If yes, describe:	Yes	No
5. Active Suicidal Ideation with Specific Plan and Intent Thoughts of killing oneself with details of plan fully or partially worked out and subject has some intent to carry it out. Have you started to work out or worked out the details of how to kill yourself? Do you intend to carry out this plan? If yes, describe:	Yes	No

INTENSITY OF IDEATION		
	t severe type of ideation (i.e., 1-5 from above, with 1 being the least severe	
and 5 being the most severe).		Most
Most Severe Ideation:		Severe
Type # (1-5)	Description of Ideation	
Frequency		
How many times have you had these thoughts?		
(1) Less than once a week (2) Once a week (3) 2-5 times in w	veek (4) Daily or almost daily (5) Many times each day	
Duration		
When you have the thoughts, how long do they last?		
(1) Fleeting - few seconds or minutes	(4) 4-8 hours/most of day	
(2) Less than 1 hour/some of the time	(5) More than 8 hours/persistent or continuous	
(3) 1-4 hours/a lot of time		
Controllability		
Could/can you stop thinking about killing yourself or wan	nting to die if you want to?	
(1) Easily able to control thoughts	(4) Can control thoughts with a lot of difficulty	
(2) Can control thoughts with little difficulty	(5) Unable to control thoughts	
(3) Can control thoughts with some difficulty	(0) Does not attempt to control thoughts	
Deterrents		
Are there things - anyone or anything (e.g., family, religio	on, pain of death) - that stopped you from wanting to die or acting on	
thoughts of committing suicide?	The state of the s	
(1) Deterrents definitely stopped you from attempting suicide	(4) Deterrents most likely did not stop you	
(2) Deterrents probably stopped you	(5) Deterrents definitely did not stop you	
(3) Uncertain that deterrents stopped you	(0) Does not apply	
Reasons for Ideation		
What sort of reasons did you have for thinking about wan	ting to die or killing yourself? Was it to end the pain or stop the way	
	with this pain or how you were feeling) or was it to get attention,	
revenge or a reaction from others? Or both?	, _f _g _g _g	
(1) Completely to get attention, revenge or a reaction from others	(4) Mostly to end or stop the pain (you couldn't go on	
(2) Mostly to get attention, revenge or a reaction from others	living with the pain or how you were feeling)	
(3) Equally to get attention, revenge or a reaction from others	(5) Completely to end or stop the pain (you couldn't go on	
and to end/stop the pain	living with the pain or how you were feeling)	
	(0) Does not apply	

SUICIDAL BEHAVIOR	Since I	Last
(Check all that apply, so long as these are separate events; must ask about all types)	Visi	it
Actual Attempt: A potentially self-injurious act committed with at least some wish to die, as a result of act. Behavior was in part thought of as method to kill oneself. Intent does not have to be 100%. If there is any intent/desire to die associated with the act, then it can be considered an actual suicide attempt. There does not have to be any injury or harm, just the potential for injury or harm. If person pulls trigger while gun is in mouth but gun is broken so no injury results, this is considered an attempt.	Yes	No
Inferring Intent: Even if an individual denies intent/wish to die, it may be inferred clinically from the behavior or circumstances. For example, a highly lethal act that is clearly not an accident so no other intent but suicide can be inferred (e.g., gunshot to head, jumping from window of a high floor/story). Also, if someone denies intent to die, but they thought that what they did could be lethal, intent may be inferred. Have you made a suicide attempt? Have you done anything to harm yourself?		
Have you done anything dangerous where you could have died? What did you do?	Total #	
Did you as a way to end your life?		
Did you want to die (even a little) when you?		_
Were you trying to end your life when you?		
Or did you think it was possible you could have died from ?		
Or did you do it purely for other reasons / without ANY intention of killing yourself (like to relieve stress, feel better, get		
sympathy, or get something else to happen)? (Self-Injurious Behavior without suicidal intent) If yes, describe:		
	Yes	No
Has subject engaged in Non-Suicidal Self-Injurious Behavior?		
Interrupted Attempt:		
When the person is interrupted (by an outside circumstance) from starting the potentially self-injurious act (if not for that, actual attempt would have	Yes	No
occurred). Overdose: Person has pills in hand but is stopped from ingesting. Once they ingest any pills, this becomes an attempt rather than an interrupted attempt. Shooting: Person has gun pointed toward self, gun is taken away by someone else, or is somehow prevented from pulling trigger. Once they pull the trigger, even if the gun fails to fire, it is an attempt. Jumping: Person is poised to jump, is grabbed and taken down from ledge. Hanging: Person has noose around neck but has not yet started to hang - is stopped from doing so.		
Has there been a time when you started to do something to end your life but someone or something stopped you before you actually did anything? If yes, describe:	Total #	
n yes, deserbe.	_	_
Aborted Attempt: When person begins to take steps toward making a suicide attempt, but stops themselves before they actually have engaged in any self-destructive behavior. Examples are similar to interrupted attempts, except that the individual stops him/herself, instead of being stopped by something else.	Yes	No
Has there been a time when you started to do something to try to end your life but you stopped yourself before you actually did anything?	Total #	# of
If yes, describe:	abort	ed
		_
Preparatory Acts or Behavior: Acts or preparation towards imminently making a suicide attempt. This can include anything beyond a verbalization or thought, such as assembling a specific method (e.g., buying pills, purchasing a gun) or preparing for one's death by suicide (e.g., giving things away, writing a suicide note). Have you taken any steps towards making a suicide attempt or preparing to kill yourself (such as collecting pills, getting a gun, giving valuables away or writing a suicide note)? If yes, describe:	Yes	No
Suicidal Behavior:	Yes	No
Suicidal behavior was present during the assessment period?		
Suicide:		No

Answer for Actual Attempts Only	Most Lethal Attempt Date:
Actual Lethality/Medical Damage: 0. No physical damage or very minor physical damage (e.g., surface scratches). 1. Minor physical damage (e.g., lethargic speech; first-degree burns; mild bleeding; sprains). 2. Moderate physical damage; medical attention needed (e.g., conscious but sleepy, somewhat responsive; second-degree burns; bleeding of major vessel). 3. Moderately severe physical damage; medical hospitalization and likely intensive care required (e.g., comatose with reflexes intact; third-degree burns less than 20% of body; extensive blood loss but can recover; major fractures). 4. Severe physical damage; medical hospitalization with intensive care required (e.g., comatose without reflexes; third-degree burns over 20% of body; extensive blood loss with unstable vital signs; major damage to a vital area). 5. Death	Enter Code
Potential Lethality: Only Answer if Actual Lethality=0 Likely lethality of actual attempt if no medical damage (the following examples, while having no actual medical damage, had potential for very serious lethality: put gun in mouth and pulled the trigger but gun fails to fire so no medical damage; laying on train tracks with oncoming train but pulled away before run over).	Enter Code
0 = Behavior not likely to result in injury 1 = Behavior likely to result in injury but not likely to cause death 2 = Behavior likely to result in death despite available medical care	

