2.3 Safety Outcome Assessments

The following assessments will establish the safety and tolerability of AUSTEDO during the AUDYT trial:

- Tolerability will be established by the proportion of study subjects able to titrate up to 48 mg/d (or up to 36 mg/d if receiving a strong CYP2D6 inhibitor) and able to complete the study at this dosage.
- Adverse events will be surveyed during all study Visits and during weekly telephone communications with the study subjects that will happen during the ramp-up period.
- AUSTEDO may prolong the QT interval. QT interval prolongation is associated with the development of tachyarrhythmias and Torsades de Pointes. To screen for the development of significant QT prolongation (defined as a corrected QT –Bazett– interval of 450 (458) milliseconds –or higher– in men or 460 (472) milliseconds –or higher– in women), a 12-lead electrocardiogram (ECG) will be performed during all scheduled study Visits, including the early termination Visit, if such a Visit happens. Should there be evidence of QT prolongation, it will remain at the investigator's discretion whether to discontinue the study drug, or to reduce the dose to a new, maximum, well-tolerated dose. A follow up ECG will be performed 1 week after the dose reduction (during an unscheduled Visit) to ensure the QTc is no longer significantly prolonged.
- A complete physical examination will be performed at the time of the initial and final study Visit, as well as during the early termination Visit, if applicable. Any and all changes in the examination happening during the trial will be recorded, and reported when appropriate.
- Vital Signs (including weight) will be measured and recorded during all scheduled study Visits, including the early termination Visit, if such a Visit happens. Any and all gross abnormalities or significant changes will be reported.
- Suicidal thoughts or actions are a possible side effect of AUSTEDO use. The Columbia Suicide
 Severity Rating Scale (C-SSRS) will be administered during all scheduled study Visits, including
 the early termination Visit, if such a Visit happens. Development of suicidality as determined by
 this instrument at any point during the trial will warrant the immediate discontinuation of the
 study drug, as well as psychiatric care as determined necessary by the investigator. Subjects
 with any signs or suicidality during Visit 1 as detected by the scale will be immediately excluded
 from participating in the trial.

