3.5.1.2 Visit 2: Ramp-up period (Week 2 +/- 2 Days)

Visit 2 will be the first one on study drug. This is a safety Visit, which will happen 5-9 days after study drug initiation. The activities to be performed during Visit 2 include:

- Adverse events will be assessed
- Vital signs
- 12-lead ECG
- C-SSRS
- SSS

Patients will be contacted on a weekly basis via telephone during the ramp-up period to assess study drug tolerability. Dose reductions will be allowed in this period at the discretion of the investigator, but also during the maintenance period. A dose reduction during the ramp-up period will determine the start of the maintenance period, as it will be assumed that the new, lower AUSTEDO dose is the maximum well-tolerated dose of AUSTEDO for that study subject. Similarly, subjects will remain on the new, maximum well-tolerated dose of AUSTEDO for the remainder of the trial once a dose reduction is done during the maintenance period.

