3.5.1.3 Visit 3: Maintenance dose starts

This is a safety Visit. The time during which this Visit will happen may vary depending on the duration of the ramp-up period, as follows:

- For subjects able to titrate up to 48 mg/day, Visit 3 will be scheduled during week 7.
- For subjects receiving a strong CYP2D6 inhibitor and, hence, able to titrate only up to 36 mg/day, Visit 3 will happen during week 5.
- For subjects with dose-limiting side effects during the ramp-up period, Visit 3 will be scheduled up to 3 days after the maximal, well-tolerated dose is established (this landmark will determine when the maintenance period has started).

The activities to be performed during Visit 3 include:

- Adverse events will be assessed
- Vital signs
- 12-lead ECG
- C-SSRS
- SSS

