3.5.2.3 Unscheduled Visit

A patient may return for an unscheduled Visit at any time at the Investigator's discretion (for example, when a one week post dose-reduction ECG is required). The procedures conducted at the unscheduled Visit may be limited, depending on the reason for the Visit (for example, for dispensing of new study drug to replace a lost bottle of study drug would only require those specific procedures relevant to the reason for the unscheduled Visit to be done).

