3.5.2.4 Dose Adjustment

Adjustments in the dose of AUSTEDO will be allowed throughout the study. If a reduction in the dose of AUSTEDO is required during the ramp-up period due to dose-limiting side effects, study subjects will be instructed to reduce the total daily AUSTEDO dose by 6 mg (1 tablet) every day until a new, maximum well-tolerated dose of AUSTEDO is established. A faster dose reduction will be allowed if deemed necessary by the investigator. Once this new dose is determined, the maintenance period will be considered initiated, and subjects will be instructed to complete Visit 3 and to remain on this dose for 6 weeks. Any side effects encountered will be recorded and reported as appropriate.

Dose-limiting toxicity will be defined in this protocol as the development of any of the following during the titration period: a) new or worsening depression, b) worsening of dystonic symptoms, c) QTc increase of >39 but <60 milliseconds from baseline, or d) any other sign or symptom that, at the PI's discretion, would preclude further safe titration of the study drug.

If a reduction in the dose of AUSTEDO is required during the maintenance period due to dose-limiting side effects, study subjects will be instructed to reduce the total daily AUSTEDO dose by 6 mg (1 tablet) every day until a new, maximum well-tolerated dose of AUSTEDO is established. A faster dose reduction will be allowed if deemed necessary by the investigator. Once this new dose is determined, subjects will be instructed to remain on this dose until the 6 weeks of the maintenance period are completed. A new maintenance period will NOT start every time a dose reduction is performed. Any side effects encountered will be recorded and reported as appropriate.

Increments in the total daily dose of AUSTEDO will not exceed 6 mg/week, as recommended by the package insert.³ Treatment interruptions will be discouraged unless necessary. In these cases, resuming AUSTEDO at the previous maintenance dose without titration will be allowed as long as the subject has been off study drug for 6 days or less. Subjects who require drug cessation for a week or more will be consider withdrawn from the trial, and will be asked to complete an early termination Visit.

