4.7 Prohibited Medications and Restrictions

Reserpine

Reserpine is an irreversible VMAT2 inhibitor, and, thus, will not be used concomitantly with AUSTEDO. In clinical practice, at least twenty (20) days must elapse after stopping reserpine before starting AUSTEDO.

Monoamine Oxidase Inhibitors

AUSTEDO is contraindicated in subjects taking MAOIs. In clinical practice, AUSTEDO will not be used in combination with an MAOI, or within 14 days of discontinuing therapy with an MAOI.

Tetrabenazine

AUSTEDO is contraindicated in subjects currently taking tetrabenazine. In clinical practice, AUSTEDO may be initiated the day following discontinuation of Tetrabenazine.

AUSTEDO is also contraindicated in subjects:

- Who are suicidal, or in subjects with untreated or inadequately treated depression.
- With hepatic impairment.
- 4.8 Concomitant Medications

Strong CYP2D6 inhibitors

As per the package insert,³ concomitant use of strong CYP2D6 inhibitors has been shown to increase the systemic exposure to the active dihydro-metabolites of AUSTEDO by approximately 3 fold. The daily dose of AUSTEDO will not exceed 36 mg per day, and the maximum single dose of AUSTEDO will not exceed 18 mg in subjects taking these inhibitors.

Table 5 below shows a list of strong CYP2D6 inhibitors:

Table 5 Strong CYP2D6 inhibitors
Bupropion
Fluoxetine
Paroxetine
Quinidine
Terbinafine

Neuroleptics

The risk for parkinsonism, NMS, and akathisia may be increased by concomitant use of AUSTEDO and dopamine antagonists or antipsychotics. As per the inclusion/exclusion criteria, subjects with a history of psychiatric disease or taking an antipsychotic (even if for a non-psychiatric reason) are not eligible for participation in the AUDYT trial.

Alcohol or other sedatives

Concomitant use of alcohol or other sedating drugs may have additive effects and worsen sedation and somnolence. As mentioned in the exclusion criteria, no change in the dose of psychoactive medications will be allowed for the duration of the trial, or at least 30 days prior to screening. Subjects will be encouraged to abstain from alcohol for the duration of the trial.

Drugs causing QTc prolongation

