- a condition detected or diagnosed after study drug administration even though it may have been present prior to the start of the study
- persistent disease or symptoms present at baseline which worsen following the start of the study

An AE does not include:

- medical or surgical procedures (e.g., surgery, endoscopy, tooth extraction, transfusion) Note: in this case, the condition that led to the procedure is an AE
- pre-existing diseases or conditions present or detected prior to start of study drug administration, which do not worsen
- the disease or disorder being studied or a sign or symptom associated with that disease (i.e., signs or symptoms associated with lack of efficacy will generally be considered to reflect underlying disease, rather than AEs)
- situations where an untoward medical occurrence has not occurred (e.g., hospitalization for elective surgery, social, and/or convenience admissions)
- overdose of either study drug or concomitant medication without any signs or symptoms

All AEs will be fully and completely recorded. The following attributes will be assigned: description of AE, dates and times of onset and resolution (or whether ongoing), severity, causality to study drug, whether an SAE or not, and action taken (i.e., no action taken; study medication interrupted; study medication discontinued; other).

In the event that a subject is withdrawn from the study because of an AE, it will be recorded. The subject will be followed and treated by the investigator until the AE has resolved or a new chronic baseline has been established. The investigator will report all directly observed AEs and all spontaneously reported AEs. At each Visit the investigator will ask the subject a nonspecific question (e.g., "Have you noticed anything different since your last Visit?") to assess whether any AEs have occurred since the last report or Visit. AEs will be identified and recorded in appropriate medical terminology.

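### Low-priority improvement: no C-SSRS is scheduled between Visit 2 and Visit 3 while the dose rises weekly, and the weekly calls already planned could carry its screening questions

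*Combined protocol and SAP*

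**What the plan says.** Sections 2.3 and 3.6.1.5 name suicidality as a possible side effect and set a mandatory response: "Development of suicidality as determined by this instrument at any point during the trial will warrant the immediate discontinuation of the study drug". The C-SSRS is given at Visits 1 to 5 and at early termination (Appendix 1). Its form (Figure 4) offers only those contacts and asks about the time since the last Visit.

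Visit 2 falls 5 to 9 days after the first dose (section 3.5.1.2). For the next Visit, section 3.5.1.3 says: "For subjects able to titrate up to 48 mg/day, Visit 3 will be scheduled during week 7". With a strong CYP2D6 inhibitor the ceiling is 36 mg/day and Visit 3 is in week 5. After dose-limiting side effects it comes within 3 days of the tolerated dose being set.

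Between these Visits contact is by telephone. Section 2.3: "Adverse events will be surveyed during all study Visits and during weekly telephone communications with the study subjects", the calls being confined to ramp-up. Section 3.5.1.2: "Patients will be contacted on a weekly basis via telephone during the ramp-up period to assess study drug tolerability". The one elicitation wording supplied is in section 5.1.1 and concerns Visits: "At each Visit the investigator will ask the subject a nonspecific question".

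Other provisions bear on the same risk:
- Section 4.7 lists as contraindicated those "Who are suicidal, or in subjects with untreated or inadequately treated depression", with no action attached.
- Dose-limiting toxicity (sections 1.3.1, 3.1 and 3.5.2.4) includes new or worsening depression, and anything that in the PI's judgment "would preclude further safe titration of the study drug".
- Section 3.5.2.3: "A patient may return for an unscheduled Visit at any time at the Investigator's discretion".
- Section 8.2 permits withdrawal of a subject for safety.

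**The concern.** The one response to suicidality that the protocol makes compulsory depends on an instrument that is not scheduled during most of the escalation. All tablets are dispensed at Visit 1 (section 4.10), so the dose keeps rising at home without a Visit. If a subject develops suicidal thoughts, does not mention them, and nobody notices on a call, the drug could be increased several more times before the C-SSRS at Visit 3.

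The other provisions do not require anyone to ask. Depression as a dose-limiting toxicity must first be detected, and no tool for that is tied to the calls. The stated response to dose-limiting toxicity is dose reduction to a tolerated level, not a stop. Unscheduled Visits and safety withdrawal are discretionary.

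**Working it through.** **Conventions.** Day 1 is the first dose, and weeks run as in Tables 3 and 4. The protocol does not state the Visit 2 to Visit 3 gap. It does state the Visit 2 window, which reproduces: 7 ± 2 = 5 to 9 days after first dose, that is, days 6 to 10.

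**Time without a scheduled C-SSRS.** Shortest gap = earliest Visit 3 − latest Visit 2. Longest gap = latest Visit 3 − earliest Visit 2.
- 48 mg path, Visit 3 on days 43 to 49: 43 − 10 = 33; 49 − 6 = 43 days.
- 36 mg path, Visit 3 on days 29 to 35: 29 − 10 = 19; 35 − 6 = 29 days.

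**Dose increases strictly between the Visits.** Steps fall on days 8, 15, 22, 29, 36 and 43 (48 mg), or 8, 15, 22 and 29 (36 mg).
- 48 mg: 4 of 6 (Visits on days 10 and 43) to 6 of 6 (days 6 and 49).
- 36 mg: 2 of 4 (days 10 and 29) to 4 of 4 (days 6 and 35).

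**Mean delay to detection.** Assume onset is uniform over the gap and nothing else detects it. Now: gap/2, giving 33/2 = 16.5 to 43/2 = 21.5 days (48 mg) and 19/2 = 9.5 to 29/2 = 14.5 days (36 mg).

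With questions on calls, mean delay = Σ(interval²)/(2 × gap). The protocol does not fix call days, so I assume dose-step days during ramp-up, counting day 8 where it follows Visit 2.

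| Path, Visit 2 and 3 days | Intervals | Mean delay (days) | Longest (days) |
|---|---|---|---|
| 48 mg, 10 and 43 | 5, 7, 7, 7, 7 | 221/66 = 3.3 | 7 |
| 48 mg, 6 and 49 | 2, 7, 7, 7, 7, 13 | 369/86 = 4.3 | 13 |
| 36 mg, 10 and 29 | 5, 7, 7 | 123/38 = 3.2 | 7 |
| 36 mg, 6 and 35 | 2, 7, 7, 13 | 271/58 = 4.7 | 13 |

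These rows are the narrowest and widest gaps. The mean is slightly higher when Visit 2 itself falls on day 8 and Visit 3 is latest: 7, 7, 7, 7, 13 gives 365/82 = 4.5 (48 mg), and 7, 7, 13 gives 267/54 = 4.9 (36 mg).

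**Expected cases in the gap.** Upper assumption: the 2% suicidal ideation on drug in the 12-week (84-day) Huntington's disease trial (section 5.1.1.2), spread evenly over time.
- 48 mg: 15 × 0.02 × 33/84 = 0.12 to 15 × 0.02 × 43/84 = 0.15.
- 36 mg, if all 15 subjects were on that path: 0.3 × 19/84 = 0.07 to 0.3 × 29/84 = 0.10.

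Lower assumption: 0, from the 117-subject tardive dyskinesia trial in section 1.2.2 (0% on drug, 1.7% on placebo).

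**For comparison, Visit 3 to Visit 4.** 48 mg: 78 − 49 = 29 to 84 − 43 = 41 days. 36 mg: 64 − 35 = 29 to 70 − 29 = 41 days.

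**The case against.** The case for leaving the plan alone is substantial. The C-SSRS is given at every scheduled Visit, with a compulsory stop. Weekly calls cover ramp-up. Section 3.4.2 excludes subjects with major depression, bipolar disorder or past suicidality. Depression identified on a call leads to dose reduction and an early Visit 3 that includes the C-SSRS. The form looks back to the previous Visit, so an honest answer at Visit 3 covers the whole gap: detection is delayed, not lost. The 2% comes from a population that the protocol describes as being at increased risk, and in the tardive dyskinesia trial the only suicidal ideation was on placebo. All of this stands, and it is why the point has low priority. What remains is that none of these routes requires the question to be asked while the dose is rising.

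A reader might infer that suicidality goes unmonitored during escalation. The documents do not support that. Adverse events are surveyed weekly, and the absence of a call script does not show that callers leave out mood.

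A reader might also infer that suicidality is handled less strictly than cognition or parkinsonism, because sections 3.6.1.7 and 3.6.1.8 allow action even at Visits where the scale is not given. That does not follow. Those clauses exist because the MMSE and MDS-UPDRS are scheduled only at Visits 1 and 4 and early termination, whereas the C-SSRS is given at every scheduled Visit. They do not mention calls, and their response is discretionary where the suicidality stop is mandatory.

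It is also fair to say that Visit 3 to Visit 4 has no scheduled calls at all, and on the 36 mg path that interval is longer than the one raised here. Questions there would need new contacts, so they are not part of a low-cost change.

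**Conclusion.** The point holds as a low-cost safety improvement of the lowest severity, not as a defect in the design. On the path to full dose, 33 to 43 days (48 mg) or 19 to 29 days (36 mg) of escalation pass with no scheduled C-SSRS and no required suicidality question. The ranges apply to subjects who reach their ceiling dose; dose-limiting toxicity shortens them.

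Using the existing calls would cut mean detection delay, at the narrowest and widest gaps, to about 3.3 to 4.3 days (48 mg) and 3.2 to 4.7 days (36 mg). This rests on uniform onset, no detection by other routes, accurate answers and calls on dose-step days. Expected cases are 0 to about 0.15 in 15 subjects, and any found by other routes would lower that. The argument therefore rests on the seriousness of the event, a stop rule the protocol already adopts, and the small cost, not on a likely number of cases.

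**What to change.** 1. In sections 2.3, 3.5.1.2 and 3.6.1.5 and Appendix 1, add the C-SSRS ideation and behavior screening questions to the existing weekly ramp-up calls, asked by someone trained on the scale.
2. On Figure 4, add a telephone/other contact option (the adverse event form in Figure 1 already has an *Other* entry) and a recall period running from the last contact.
3. Extend the immediate-stop rule to suicidality identified by any route at any time, with investigator contact the same day and an unscheduled or early termination Visit.

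No new call or routine Visit is needed. On the assumed call days, 4 to 5 existing calls per subject (48 mg) or 2 to 3 (36 mg) become longer. The maximum is 15 × 5 = 75 calls: 6.25 hours in total at an assumed 5 minutes each, 12.5 hours at 10 minutes. The scale is rater- or clinician-administered, and the protocol does not say who makes the calls, so training may be needed. An investigator must be reachable the same day, each positive screen leads to a Visit, and one amendment is required. The Visit 3 to Visit 4 interval (29 to 41 days) gains only the any-route stop wording.
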